3.1.1. Follow-up Procedures

The subjects will be followed until 180 days after start of treatment. Subjects who lose their graft during the course of the study will remain in the study and be followed according to the study protocol and clinical practice at the site.

After study completion, all study subjects will be followed regularly by the nephrologist or transplant surgeons according to each centre's follow-up routines for transplanted subjects. The frequency of outpatient visits will be adjusted individually to the state of patient health and transplant function.

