12. STATISTICAL METHODS

The statistical analyses will be outsourced to a CRO. Prior to clean file, a Statistical Analysis Plan (SAP) with details on statistical analysis and data presentation will be established. No formal statistical hypothesis testing will be performed in this study.

Summary tables will in general be presented by treatment and total unless this is not appropriate for specific tables. Mean figures will similarly be presented by treatment.

Summary statistics for continuous variables will in general be presented as n, arithmetic mean, standard deviation, median, minimum and maximum. When continuous data are recorded at different time points absolute values at each time point and, if relevant, changes from baseline may be presented.

For categorical data frequencies and percentages will be presented.

Due to the exploratory nature of the study, missing data will remain missing and no adjustment will be implemented.

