3.1 Full Analysis Set

FAS will consist of all patients treated with any amount of study medication. Patients will contribute to the analysis ‘as randomized’.

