4.1.4 Data imputation

In general, missing data will remain as missing and the missing values will not be adjusted. There are some exceptions described below.

Adverse events

Missing values will be treated as missing except for causality, toxicity, intensity, seriousness and outcome of an AE, in which case a “worst case” approach will be taken. If causality is missing, it will be set to “related”. If intensity is missing, it will be set to “severe”. If seriousness is missing, it will be considered as a Serious Adverse Event (SAE). If outcome is missing and no date is given for the outcome it will set to “not yet recovered”.

Dates for adverse event and concomitant medication

Missing or partial start dates for AEs and concomitant medication data will be handled in the following way:

- If the start date is totally missing, the date will still be missing.
- If the start date is partial where only months and year are given, then the two cases are considered:
 - 1 If the available partial date (month and year) is before the month and year of treatment start date, then the AE/medication will be considered as pre-treatment and the date will be imputed as the start (1st) of the month.
 - 2 If the available partial date does not indicate that the AE/medication has started before the treatment start, then the AE/medication will be considered as treatment emergent/concomitant. The date will be imputed as the start (1st) of the month (if the month is not same as that of the treatment start date) or treatment start date (if the month is same as the treatment start date).
- If the start date is partial where only the year is given, then the two cases are considered:
 - 3 If the available partial date (year) is clearly before the year of treatment start date, then the start date is imputed as start of the year (1st January YYYY).
 - 4 If the available partial date (year) is equal to or after the year of treatment start date, then the start date will be imputed as start of the year (1st January YYYY) (if the year is not same as that of the treatment start date) or treatment start date (if the year is same as the treatment start date).

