In addition, the reduction of total serum IgG levels will be analyzed as a binary endpoint. The binary endpoint is defined as a success, if the minimum IgG value at any time point during the 5 days following the start of treatment is less than 5% of baseline for the patient. The proportion of patients, which satisfy the success criterium, will be presented in a summary table by treatment. The difference in proportion between the two treatments will be presented with a 95% CI in a summary table. The 95% CI for the difference between the two treatments will be based on exact Confidence Limits. In addition, the proportion of patients which satisfy the success criterium will be presented by treatment and time point.

The composition of IgG-fragments will be analyzed centrally using SDS-PAGE. Each sample will be assigned a score depending on the observed composition of fragments as follows:

- 0=no intact IgG, scIgG or F(ab')₂
- 1=only F(ab')₂
- 2=mix of scIgG and F(ab')₂
- 3=only scIgG
- 4=mix of intact IgG and scIgG
- 5=only intact IgG

SDS-PAGE scores will be summarized by time point.

Presence of intact IgG on SDS-PAGE until start of IVIg treatment

The endpoint is a success for a patient if no detectable intact IgG is found by the SDS-PAGE assay for at least one time point between the start of study medication (imlifidase) treatment and start of administration of IVIg. No detectable intact IgG is defined as SDS-PAGE scores 0, 1, 2 or 3. The

proportion of patients, who reached the success criterium, will be summarized in a table using the PKS set.

Number of patients with resolution of AMR at day 180

The number of patients with resolution of AMR at day 180 will be handled as a binary variable. Resolution is defined as “Active AMR” or “Chronic active AMR” not being selected from the biopsy protocol.

The endpoint is a success if the patients have resolution of AMR at day 180. The proportion of patients, which satisfy the success criterium, will be tabulated by treatment. A list will be created by patient. The FAS set will be applied.

Patient survival at day 180

The patient survival on day 180 will be handled as a binary variable.

The endpoint is a success if the patients have survived on day 180. The proportion of patients, which satisfy the success criterium, will be summarized and listed by patient. The FAS set will be applied.

Pharmacokinetic

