14.1.7	Table	Exposure (FAS)
EFFICACY DATA		
14.2.1	Table	Difference in maximum DSA reduction and 95% CI (FAS)
14.2.2	Table	Difference in maximum DSA reduction and 95% CI (PPS)
14.2.3	Table	DSA reduction - by time point (FAS)
14.2.4	Table	DSA reduction - by time point (PPS)
14.2.5	Table	MFI levels for DSA c1q - by time point (FAS)
14.2.6	Table	Proportion of patients with absence of graft loss at day 180 (FAS)
14.2.7	Table	Proportion of patients having no signs of transplant glomerulopathy at day 180 (FAS)
14.2.8	Table	Kidney biopsy (Banff) - Scores - by time point (FAS)
14.2.9	Table	Kidney biopsy (Banff) - Change from baseline (scores) - by time point (FAS)
14.2.10	Table	Kidney biopsy (Banff) - Interpretations - by time point (FAS)
14.2.11	Table	Kidney biopsy (Banff) - Shift table - by time point (FAS)
14.2.12	Table	Kidney biopsy () - Scores - by time point (FAS)
14.2.13	Table	Kidney biopsy () - Change from baseline - by time point (FAS)
14.2.14	Table	Number of sessions of PE and IA for 180 days (FAS)
14.2.15	Table	Total IgG - by time point (FAS)
14.2.16	Table	Proportion of patients having reduction in total IgG - by time point (FAS)
14.2.17	Table	Composition of IgG-fragments (SDS-PAGE) - by time point (FAS)
14.2.18	Table	Proportion of patients having no detectable intact IgG (PKS)
14.2.19	Table	Proportion of patients with resolution of AMR at day 180 (FAS)
14.2.20	Table	Patient survival at day 180 (FAS)
14.2.21	Table	Summary of imlifidase (PK) concentrations - by time point (PKS)
14.2.22	Table	Summary of imlifidase PK parameters (PKS)
DISPLAYS OF ADVERSE EVENTS		
14.3.1	Table	Overview of treatment-emergent AEs (SAF)
14.3.2	Table	Summary of treatment-emergent AEs - by SOC and PT (SAF)
14.3.3	Table	Summary of treatment-emergent AEs - by causality (SAF)

14.3.4	Table	Summary of treatment-emergent AEs - by intensity (SAF)
14.3.5	Table	Summary of related treatment-emergent AEs - by intensity (SAF)
14.3.6	Table	Summary of SAEs (SAF)
14.3.7	Table	Summary of SAEs - by causality (SAF)
14.3.8	Table	Summary of treatment-emergent SAEs (SAF)
14.3.9	Table	Summary of treatment-emergent SAEs - by causality (SAF)
14.3.10	Table	Summary of treatment-emergent SAEs leading to death (SAF)
14.3.11	Table	Summary of treatment-emergent AEs leading to withdrawal (SAF)
DISPLAYS OF SAFETY DATA		
14.4.1	Table	Summary of clinical chemistry variables - by time point (SAF)
14.4.2	Table	Summary of haematology variables - by time point (SAF)

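### AMR resolution at Day 180 does not require a read Day 180 biopsy, so a patient whose graft is lost without one is either excluded or, on the literal wording, a success

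*SAP*

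**What the plan says.** SAP 4.6.2 treats resolution of AMR at Day 180 as a binary variable. A patient is resolved when neither Active AMR nor Chronic active AMR is recorded, which the SAP words as those categories "not being selected from the biopsy protocol". On presentation it says: "The proportion of patients, which satisfy the success criterium, will be tabulated by treatment". The analysis set is the FAS, both in that section and in the title of Table 14.2.19 (SAP section 8). Under SAP 3.1, "FAS will consist of all patients treated with any amount of study medication"; having a biopsy is not a condition.

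For missing values, SAP 4.1.4 says: "In general, missing data will remain as missing and the missing values will not be adjusted". It adds "There are some exceptions described below", but the exceptions cover only adverse event attributes and the dates of adverse events and concomitant medication. Protocol section 12 has the same general rule: "missing data will remain missing and no adjustment will be implemented".

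Protocol 12.3.8 asks only for a count of resolved patients and gives no definition. Graft loss and survival are separate binary endpoints in SAP 4.6.2, and neither is linked to AMR resolution. Protocol 3.1.1 says that patients who lose their graft "will remain in the study and be followed according to the study protocol and clinical practice at the site". SAP section 5, which lists departures from the protocol analysis, does not mention this endpoint.

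**The concern.** The endpoint is defined by something not being recorded, in a set that includes patients for whom nothing may have been recorded. Graft loss does not always prevent a Day 180 biopsy, since these patients stay in follow-up and one who has returned to dialysis may still have the graft. Transplantectomy, which is part of the SAP's definition of graft loss, does prevent it, and so does death.

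Such missing biopsies are unlikely to be neutral. Protocol 1.1 describes persistent DSA as leading, through transplant glomerulopathy, to graft failure. The patients without a biopsy may therefore include the worst outcomes of the rejection being assessed. A coding that drops them, or counts them as resolved, flatters the arm with proportionally more of them. The study is open-label (SAP 2.3), so a rule left until the tables are programmed would be chosen with arm and outcome known.

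**Working it through.** **The plan's own figures.** The documents give no expected rate of resolution, graft loss or death, so there is no figure for this endpoint to reproduce. The one design figure, the 95% CI about 8 points wide in SAP 2.2, concerns the primary endpoint and does not bear on this point.

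**Inputs from the documents.** 20 imlifidase and 10 PE patients (SAP 2.4).

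**Notation.** In an arm of n patients, r are resolved on a read Day 180 biopsy and m have no Day 180 biopsy because of graft loss. The possible codings are:

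- Non-success: r/n. This results if the proportion is taken over all FAS patients and only resolved biopsies count. It would also turn refusals and inadequate samples into failures.
- Excluded: r/(n − m). This follows from missing values staying missing.
- Success: (r + m)/n. This follows from the literal wording.

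**Effect of one affected patient (m = 1), relative to non-success.**

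- Success: 1/n, which is 1/20 = 5 points for imlifidase and 1/10 = 10 points for PE.
- Excluded: r/(n − 1) − r/n = r/[n(n − 1)]. For imlifidase this is r/380 with r from 0 to 19, so 0 to 5 points. For PE it is r/90 with r from 0 to 9, so 0 to 10 points.

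**Effect on the difference, imlifidase minus PE.** All values of r and m below are assumed.

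| Case | Imlifidase r, m | PE r, m | Non-success | Excluded | Success |
|---|---|---|---|---|---|
| 1. Losses in PE only | 10, 0 | 4, 2 | 50 − 40 = +10 | 50 − 50 = 0 | 50 − 60 = −10 |
| 2. Losses in imlifidase only | 8, 4 | 5, 0 | 40 − 50 = −10 | 50 − 50 = 0 | 60 − 50 = +10 |
| 3. Losses in PE only | 9, 0 | 4, 2 | 45 − 40 = +5 | 45 − 50 = −5 | 45 − 60 = −15 |
| 4. Equal loss proportions (20%) | 8, 4 | 4, 2 | 40 − 40 = 0 | 50 − 50 = 0 | 60 − 60 = 0 |
| 5. Equal loss proportions (10%) | 9, 2 | 5, 1 | 45 − 50 = −5 | 50 − 55.6 = −5.6 | 55 − 60 = −5 |

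Cases 1 and 2 show that the shift can favour either arm. Case 3 shows a change of sign between non-success and exclusion alone, without relying on the success coding. In cases 4 and 5 the loss proportions are equal, and the difference is unchanged or barely moves.

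**The case against.** The strongest reply is that selecting a category from a biopsy form presupposes a biopsy. SAP 4.6.2 lists the possible overall interpretations, including No rejection, so a biopsy that was read yields a positive entry and one never taken yields none. The Day 180 biopsy is scheduled, and the general rule leaves a missing result missing. This largely stands. A reader might infer that the SAP will count patients who lost their graft or died as resolved, but the documents do not say so, and exclusion is the more natural reading. Exclusion still raises the arm's rate relative to non-success whenever any other patient in that arm resolved, so the reply narrows the concern without removing it.

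A second reply concerns importance. The endpoint is descriptive, with no planned test or confidence interval. It is not among the secondary endpoints in Protocol 2.2.2; the SAP adds it in 1.1.2. All patients also receive steroids, high-dose IVIg and rituximab (Protocol 5.3), so it does not isolate the effect of removing DSA. Listings 16.2.1.5 (graft loss), 16.2.1.7 (biopsy scores and diagnosis), 16.2.1.12 (resolution) and 16.2.1.13 (survival) let a reader largely rebuild each coding. All of this stands and limits the weight of the point. It does not tell a reader of Table 14.2.19 which coding produced the headline proportion.

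A third reply is that counting death as unresolved rejection is a debatable composite, because a patient may die with a functioning graft. This stands for deaths without graft loss, and the fix treats them separately.

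**Conclusion.** The gap is real and should be closed before database lock. As written, the SAP makes a graft lost without a Day 180 biopsy either a literal success or, more naturally, an exclusion. Relative to non-success, each such patient raises the imlifidase rate by 5 points if coded as success or by 0 to 5 if excluded. For PE the figures are 10, and 0 to 10. Uneven losses can change the between-arm difference or reverse its sign; equal loss proportions can leave it unchanged.

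The per-patient figures rest on the planned 20 and 10 patients. The between-arm cases also rest on assumed numbers of resolutions and losses, as the documents give none. A reader might infer that the endpoint is biased towards imlifidase. The documents do not support that, because the direction depends on which arm has proportionally more losses without a biopsy. Neither the primary endpoint nor the sample size is affected.

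**What to change.** In SAP 4.6.2:

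- State that success requires a Day 180 biopsy of the study graft that was read and shows neither Active AMR nor Chronic active AMR.
- Count graft loss before Day 180 with no Day 180 biopsy as non-success.
- Leave other missing biopsies (refusal, inadequate sample, withdrawal) missing.

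In Table 14.2.19, by arm:

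- Show the number without a Day 180 biopsy by reason: graft loss, death or other.
- Show the biopsied-only proportion with its denominator.
- Show deaths without graft loss both as missing and as non-success.

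For transplant glomerulopathy, whose success is also defined by absence, show the biopsied denominator by arm. Record the graft-loss rule in SAP section 5, since it departs from the general missing-data rule.

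The cost is SAP wording and modest programming. Graft loss and survival are already analysed for Tables 14.2.6 and 14.2.20. The documents do not say that the reason for a missing biopsy is recorded, so this must be confirmed or queried with sites. The downside is that the endpoint becomes partly a composite with graft loss; the biopsied-only result keeps that visible.

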4.6.3 Additional analyses

No additional analyses are applied.

4.7 Safety

Safety parameters will be evaluated for the safety analysis data set.

4.7.1 Adverse events

Adverse events (AEs) will be classified according to the latest effective version of MedDRA.

A treatment emergent adverse event (TEAE) is any adverse event occurring after the administration of the IMP and within the time of residual drug effect, or a pre-treatment adverse event or pre-existing medical condition that worsens in intensity after administration of the IMP and within the time of residual drug effect.

The time of residual drug effect is the estimated period after the administration of the IMP, where the effect of the product is still considered to be present based on pharmacokinetic, pharmacodynamic or other substance characteristics. The residual drug effect is generally accepted to be 5 times the terminal half-life. The terminal half-life of imlifidase is expected to be within the range of approx. 100 hours, i.e. in this study the residual drug effect is likely to be well within the 29 Day assessments. All AEs occurring up to Day 29 are regarded as treatment emergent.

An AE overview summary table will be prepared including the number of patients reporting an AE, the percentage of patients (%) with an AE, and the number of events (E) reported for the following categories:

- TEAEs
- Related TEAEs (TEAEs considered to be possibly or probably related to IMP as judged by the investigator)
- Related Serious TEAEs
- Deaths
- Treatment-emergent Serious Adverse Events (SAEs)
- TEAEs leading to withdrawal
- Severe and life-threatening AEs

Treatment-emergent AEs will be summarised in a table by dictionary level, i.e., System Organ Class (SOC) and Preferred Term (PT) for MedDRA. The table will display the total number of patients reporting a TEAE, the percentage of patients (%) with a TEAE and the number of events (E) reported. TEAEs will be presented by SOC sorted alphabetically and PT sorted in decreasing frequency of occurrence. For the summary tables the SAF set will be applied.

Summary tables will be prepared for:

- All TEAEs
- TEAEs by causality (related/unrelated)
- TEAEs by intensity
- Related TEAEs by intensity
- SAEs
- SAEs by causality (related/unrelated)
- Treatment-emergent SAEs
- Treatment-emergent SAEs by causality (related/unrelated)

- Treatment-emergent SAEs leading to death
- TEAEs leading to withdrawal

Data listings will be provided for:

- All TEAEs sorted by patient number
- All TEAEs sorted by MedDRA SOC and PT
- SAEs
- Treatment-emergent SAEs
- Treatment-emergent SAEs leading to death
- TEAEs leading to withdrawal
- Pre-treatment emergent AEs
- Post-treatment emergent AEs

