5.2. Control treatment

The control treatment in this study is PE which is a treatment with no active substance and thus not an IMP. PE will be prepared and performed according to the standard of care at each site. 5-10 sessions of PE will be performed.

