9. ADVERSE EVENTS AND SERIOUS ADVERSE EVENTS

9.1. Definitions

9.1.1. Adverse event

An AE is the development of an undesirable medical condition or the deterioration of a pre-existing medical condition following or during exposure to a pharmaceutical product, whether or not considered causally related to the product. Relationship to the study drug will be deemed as not related, unlikely, possible or probable. An undesirable medical condition can be symptoms (e.g., nausea and chest pain), signs (e.g., tachycardia and enlarged liver) or the abnormal results of an investigation (e.g., laboratory findings and ECGs).

In cases of surgical or diagnostic procedures, the condition/illness leading to such a procedure is considered as the AE rather than the procedure itself.

In case of a fatality, the cause of death is considered as the AE, and the death is considered as its outcome.

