9.2.1.1. Causality Assessment

For each reported AE, the investigator will make an assessment of the relationship of the event to study procedures and/or IMP using the following criteria.

- **Unrelated:** applicable to an AE that occurs when the subject was not exposed to study treatment or another cause is obvious.
- **Unlikely to be related:** applicable to an AE that meets the following criteria
 - Does not follow a reasonable temporal sequence from study drug dosing
 - May readily have been produced by the subject's clinical state, environmental, or toxic factors, or other therapy administered to the subject
- **Possibly related:** applicable to AEs where connection with dosing of study drug appears unlikely but cannot be ruled out. Applicable to AEs where:

- It follows a reasonable temporal sequence dosing with study drug
- It follows a known pattern of response to study drug dosing (based on animal studies)
- **Probably related:** applicable to AEs that are considered, with a high degree of certainty, to be related to the study drug. Applicable to AEs where
 - It follows a reasonable temporal sequence study drug dosing
 - It cannot be reasonably explained by the known characteristics of the subject's clinical state, environmental or toxic factors, or other modes of therapy
 - It follows a known pattern of response to study drug dosing (based on animal studies).
- For SAEs, causal relationship will also be assessed for any study procedure.

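### The SAP counts an adverse event as related only if it is related to the IMP, which plasma exchange is not, so the by-arm related-event outputs are one-sided as written

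*SAP*

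**What the plan says.** SAP 4.7.1 lists seven categories for the adverse event overview table. One is defined as "Related TEAEs (TEAEs considered to be possibly or probably related to IMP as judged by the investigator". No other definition of related appears in the SAP. The by-causality tables are described only as splitting events into related and unrelated.

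Protocol 5.2 says of the comparator: "The control treatment in this study is PE which is a treatment with no active substance and thus not an IMP".

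The protocol's causality text is wider than the SAP's in one place and narrower in others:

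- Protocol 9.2.1.1 says that for each reported event "the investigator will make an assessment of the relationship of the event to study procedures and/or IMP using the following criteria".
- It adds: "For SAEs, causal relationship will also be assessed for any study procedure".
- Protocol 9.1.1 words the scale by drug: "Relationship to the study drug will be deemed as not related, unlikely, possible or probable".

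SAP 3.3 puts patients treated with either imlifidase or PE into the safety set and calls both study medication. SAP 4.1.1 presents summary tables by treatment group as a rule. SAP 4.1.4 sets missing causality to related.

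**The concern.** Safety and tolerability of imlifidase compared with PE is a secondary objective (Protocol 2.1.2, SAP 1.1.1). The related-event outputs are produced on a safety set that holds both arms, and by default in columns by arm. If related means related to the IMP, and only the imlifidase arm is assigned an IMP, one column can fill and the other cannot, whatever harm PE causes. A reader could take a nearly empty PE column as evidence that PE is well tolerated, when the definition produced it.

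The SAP also drops the study-procedures half of the protocol's causality assessment, and SAP section 5, which lists deviations from the protocol analysis, does not mention this.

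**Working it through.** The plan gives no figure to reproduce. The check sets the passages side by side and counts the outputs that depend on the definition.

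**Step 1: what counts as related.** The SAP rule is possibly or probably related to the IMP. By Protocol 5.2, PE is not an IMP, which leaves imlifidase as the only one. Under the rule, a patient who received PE and no imlifidase cannot have an event judged related.

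**Step 2: what the PE arm can show.** The plan has 20 imlifidase and 10 PE patients, so the PE arm is 10/30 = 33% of the study. On the wording alone, 0 of those 10 patients can have an event recorded as related by judgement. The only route in is SAP 4.1.4, which turns missing causality into related. That is an imputation, not an attribution to PE. The imlifidase arm has no such ceiling.

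**Step 3: PE in the imlifidase arm.** Protocol 5.3 allows for PE given for medical reasons in that arm. Harm from it would not be related under the rule either.

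**Step 4: does another SAP sentence mend it?** SAP 4.7.1 also ties the TEAE definition to the IMP, but then declares all events up to Day 29 treatment emergent, which brings PE-arm events into the TEAE tables. That sentence settles timing. No matching sentence settles relatedness.

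**Step 5: outputs affected** (SAP section 8, Tables 14.3.1 to 14.3.11, 11 in all):

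| How the definition reaches the output | Output |
|---|---|
| Stated for it | 'Related TEAEs' row of 14.3.1; Table 14.3.5 |
| If carried over | 'Related Serious TEAEs' row of 14.3.1; Tables 14.3.3, 14.3.7, 14.3.9 |
| Relatedness not used | Other rows of 14.3.1 (7 − 2 = 5); Tables 14.3.2, 14.3.4, 14.3.6, 14.3.8, 14.3.10, 14.3.11 (6) |

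Tables that use relatedness somewhere: 14.3.1, 14.3.3, 14.3.5, 14.3.7 and 14.3.9, which is 5; 5 + 6 = 11.

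**The case against.** The strongest reply is that the documents use these terms loosely and mean the randomised treatment. SAP 3.3 calls PE study medication. SAP 4.5 places doses or sessions together under drug exposure. The pre-treatment and TEAE definitions are tied to the IMP for both arms, which makes sense only if IMP is shorthand. The SAP rule also defers to the investigator's judgement, so the tables will report whatever the CRF field holds. The study is descriptive, and in an open-label trial the unattributed event counts are the safer basis for comparing arms.

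Much of this stands. The shorthand reading is plausible, the CRF is not shown, and PE-arm events are not lost from the other tables. But Protocol 5.2 says expressly that PE is not an IMP, and a programmer following the SAP has no instruction to read it otherwise. If the CRF does capture PE causality, the SAP definition misdescribes the data.

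A reader might infer something stronger: that the protocol itself bars PE from being judged causal. The possible category is "applicable to AEs where connection with dosing of study drug appears unlikely but cannot be ruled out" and the probable category is "applicable to AEs that are considered, with a high degree of certainty, to be related to the study drug". The unlikely category mentions "environmental, or toxic factors, or other therapy administered to the subject", and Protocol 5.7 names PE among other therapies to be recorded. The documents do not support that inference. Protocol 9.2.1.1 opens by applying its criteria to study procedures as well as the IMP. Its unrelated category turns on exposure to study treatment, and Protocol section 5, on study treatments, includes PE as the control. Protocol 5.7 is an instruction for recording concomitant therapy. No passage links it to the causality scale or tells investigators to grade PE events as unlikely.

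**Conclusion.** The point holds as a defect in the SAP's definition. As written, one row of Table 14.3.1 and Table 14.3.5 can show imlifidase-caused events but not PE-caused ones. If the definition is carried over, so do one more row of 14.3.1 and Tables 14.3.3, 14.3.7 and 14.3.9. Those outputs cannot serve the comparison with PE in that form. The all-TEAE, SAE, death and withdrawal outputs and the all-TEAE intensity table remain comparable on this point, and the primary endpoint is not touched.

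This rests on taking IMP in SAP 4.7.1 in the sense of Protocol 5.2. It would be wrong to conclude that the reported PE column will in fact be empty: investigators may have recorded PE-related events as related under Protocol 9.2.1.1. The size of any distortion in the percentages cannot be derived from the documents.

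**What to change.** In SAP 4.7.1:

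1. Define related as possibly or probably related to the study treatment received, meaning imlifidase, or PE or the immunoadsorption that Protocol 1.2 allows in its place. This agrees with SAP 3.3 and Protocol 9.2.1.1. Apply it to Tables 14.3.1, 14.3.3, 14.3.5, 14.3.7 and 14.3.9.
2. If the CRF holds only relatedness to imlifidase, title those outputs as related to imlifidase and do not present them as a comparison with PE.
3. Footnote, by arm, the number of events whose causality was imputed.
4. Record the change in SAP section 5.

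The cost is SAP wording, table titles and a footnote. The downside is possible causality queries for non-serious PE-arm events if the first option is taken and the CRF field is ambiguous. The relabelling in item 2 needs no new data.
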